8.6.3. Pregnancy

Any pregnancies reported during the study will be summarized in case narratives. Any pregnancy complication or elective termination of a pregnancy for medical reasons will be recorded as an AE or SAE and included in summaries and listings of AEs/SAEs.

9. OTHER ANALYSES

9.1. Other Analyses

This is an open-label study and the efficacy will be assessed in an exploratory manner. Therefore, no efficacy endpoint is defined and the efficacy will be assessed as other endpoints. No statistical analyses (using statistical models or tests) will be planned in this RAP. Only summary tables or listings will be provided.

9.1.1. Overview of Planned Other Analyses

The other analyses will be based on “ITT” population, unless otherwise specified. All outputs unless specified otherwise will be produced for the interim analysis and final analysis.

Summary statistics for absolute value and change from baseline will be provided for following endpoints at visit 2 (Week 0), 5 (Week 24) and 6 (Week 52) by dose group and total.

- Trough Forced Expiratory Volume in 1 second (FEV₁)
- ACQ-7 total score
- St. George's Respiratory Questionnaire (SGRQ) total score
- Asthma Quality of Life Questionnaire (AQLQ) total score

ACQ-6 will be measured at visit 1 for eligibility criteria. ACQ-6 will not be summarized in other analyses, but in demographic and baseline characteristics, see Section 6.1.3.

Summaries of all-cause unscheduled asthma related healthcare resource utilization over 52 weeks of the treatment period will be provided in only final analysis. Total below means total number of contacts across all participants.

- Unscheduled healthcare utilization (Yes or No)
- Number of telephone call (n, 0, 1, 2, 3, >3, Total)
- Number of home visit (day) (n, 0, 1, 2, 3, >3, Total)
- Number of home visit (night) (n, 0, 1, 2, 3, >3, Total)
- Number of physician office/practice visits (n, 0, 1, 2, 3, >3, Total)
- Number of urgent care / outpatient clinic visits (n, 0, 1, 2, 3, >3, Total)
- Number of emergency room visits (n, 0, 1, 2, 3, >3, Total)
- Number of inpatient hospitalisation days (ICU) (n, 0, 1, 2, 3, >3, Total)
- Number of inpatient hospitalisation days (General ward) (n, 0, 1, 2, 3, >3, Total)
- Was this contact due to an exacerbation (Yes or No)

Summary of annualized rate of severe asthma exacerbations and annualized rate of moderate/severe asthma exacerbations will be provided (only the number of participants and calculated annualized rate will be provided for this summary). Annualized rate for a given dose group will be calculated as follows, but only at final analysis:

- Summation of (total number of exacerbations) for all participants in a given dose group (or all participants for total) is divided by summation of ((date of Visit 7 / EOT visit or EW visit – treatment start date +1) / 365) for all participants in a given dose group (or all participants for total).

As for asthma exacerbations, following information will be provided.

- Number of events
 - Hospitalization
 - Emergency room visit
 - Systemic/oral corticosteroid use
 - Outcome (Resolved, Fatal or Not Resolved)
 - Duration (days), which will be calculated as Date of Outcome – Date of Onset + 1. If Outcome is Not resolved, then duration will be missing
- Number of participants with events (0, 1, 2, >2)
 - Severe
 - Hospitalization
 - Emergency room visit
 - Systemic/oral corticosteroid use
 - Moderate

11. APPENDICES

11.1. Appendix 1: Protocol Deviation Management and Definitions for Per Protocol Population

Per Protocol Population is not defined in this study.

CONFIDENTIAL

207236

11.2. Appendix 2: Schedule of Activities

11.2.1. Protocol Defined Schedule of Events

Procedure	Pre-screen	Run-in	Treatment period							Follow-up
Visit	0	1 Screening	2 Baseline	3	4	5	6	7 End of Treatment (EOT)	Early Withdrawal (EW)	Safety follow-up contact
Day	-28 to -14	-14	1	29	85	169	253	365		
Week	-4 to -2	-2	0	4	12	24	36	52		
Window		-3		-5/+2d	-5/+2d	-5/+2d	-5/+2d	-5/+2d		
Informed consent ¹	X									
Genetics/Pharmacogenetic informed consent ²	X									
Inclusion and exclusion criteria		X	X							
Demography	X									
Past and current medical conditions including asthma history ³ and exacerbation history		X								
Smoking history and status		X								
Concomitant medication review		X	X	X	X	X	X	X	X	X
Allocation/registration ⁴			X							
Register visit in IRT (RAMOS NG) ⁵	X	X	X	X	X	X	X	X	X	X
Safety Assessment										
Physical examination		X				X		X	X	
Weight/height		X								
Adverse events			X	X	X	X	X	X	X	X
Serious adverse events	X	X	X	X	X	X	X	X	X	X
Vital signs (blood pressure and pulse rate)		X	X	X	X	X	X	X	X	
ECG		X		X		X		X	X	
Hematology and clinical chemistry		X			X	X		X	X	
Urinalysis		X			X	X		X	X	
Serum pregnancy test		X ⁶			X ⁶	X ⁶		X ⁶	X ⁶	
Urine pregnancy test ⁶			X	X			X			

CONFIDENTIAL

207236

Procedure	Pre-screen	Run-in	Treatment period							Follow-up
Visit	0	1 Screening	2 Baseline	3	4	5	6	7 End of Treatment (EOT)	Early Withdrawal (EW)	Safety follow-up contact
Day	-28 to -14	-14	1	29	85	169	253	365		
Week	-4 to -2	-2	0	4	12	24	36	52		
Window		-3		-5/+2d	-5/+2d	-5/+2d	-5/+2d	-5/+2d		
Other Assessment										
ACQ ⁷		X ⁸	X ⁹			X ⁹		X ⁹	X ⁹	
SGRQ ⁷			X			X		X	X	
AQLQ ⁷			X			X		X	X	
Pre-dose spirometry ¹⁰			X			X		X	X	
Moderate/severe asthma exacerbation			X	X	X	X	X	X	X	X
Genetics/Pharmacogenetic sampling ¹¹			X							
Dispense paper Medical Problems/Medications Taken worksheet	X	X	X	X	X	X	X	X	X	
Review paper Medical Problems/Medications Taken worksheet		X	X	X	X	X	X	X	X	X
Healthcare resource utilization			X	X	X	X	X	X	X	
Dispense investigational product			X	X	X	X	X			
Collect investigational product				X	X	X	X	X		X
Dispense salbutamol (as required)		X	X	X	X	X	X			
Collect salbutamol (as required)			X	X	X	X	X	X	X	

1. The Informed Consent Form (ICF) must be signed before any study procedures, including medication cessation.
2. Genetics/Pharmacogenetic research consent may be obtained at the same time as the study Informed Consent and must be obtained prior to obtaining a Genetics/pharmacogenetic blood sample.
3. The assessment of asthma history will include: the age of the subject when they were first provided with an inhaler for asthma; completion of an asthma medical history questionnaire (a copy of this questionnaire and instructions for its use can be found in the SRM).
4. Subjects must not be allocated prior to confirming their eligibility to participate in the study.
5. The IRT will be used for allocation, and study treatment supply management (Please refer to the RAMOS NG IRT manual and SRM for more information).
6. Assessments are only to be conducted in females of reproductive potential.
7. Assessment(s) to be completed before any study procedures .Study treatment should be administered at the same time of day each applicable clinic visit,
8. Assessment to be conducted by using ACQ-6
9. Assessment to be conducted by using ACQ-7

CONFIDENTIAL

207236

10. Spirometry to be performed after withholding rescue medication for at least 6 hours and prior to taking the morning dose of study treatment. Pre-dose spirometry assessments should be performed at the same time of day at each applicable visit.
11. Pharmacogenetic sample may be drawn any time from Visit 2 onwards.

ACQ: Asthma Control Questionnaire, AQLQ: Asthma Quality of Life Questionnaire, IRT: Interactive Response Technology, SGRQ: St. George's Respiratory Questionnaire

11.3. Appendix 3: Assessment Windows

11.3.1. Clinical visits

Clinic visits are scheduled to take place as specified in the protocol. Measurements outside visit windows will not be excluded from analyses on any population.

For all clinic visits, nominal visits will be used for reporting.

All unscheduled visits will be included in listings.

11.3.2. Definitions of Assessment Windows for Adverse Events in Treatment Period

Definition of assessment windows is different among dose groups. Day 1 is defined as the study treatment start day. Section 11.3.2.1 and Section 11.3.2.2 are applicable only AE summaries by period (i.e., All AEs for week 0-12 and week 13-24 during treatment period in interim analysis, and All AEs for week 0-12, week 13-24, week 25-36 and week 37-52 during treatment period in final analysis). Section 11.3.2.3 is applicable for the approach “by dose at AE”.

11.3.2.1. In Interim Analyses

In interim analyses, the table below will be applied (i.e., data up to the day before visit 5 (week 24 visit) will be used for AE/SAE related analyses).

Analysis Window		Analysis Timepoint
Beginning Timepoint	Ending Timepoint	
Day 1	Day 84	Week 0-12
Day 85	The day before visit 5 (week 24 visit) Or Day 168 (only for participants who withdraw early)	Week 13-24

Note that the data except for AE/SAEs up to the day OF visit 5 (week 24 visit) will be used in interim analyses. This means data except for AE/SAEs (e.g., clinical laboratory) will include visit 5 (week 24 visit), but data for AE/SAEs will not include the day of visit5 (week 24 visit) in interim analyses.

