3. PLANNED ANALYSES

3.1. Interim Analyses

No statistical interim analysis requiring any hypothesis tests is planned. However, the data will be summarized when all participants (who have not withdrawn) have completed 24-week administration of IP during the treatment period and the CRF data up to Week 24 for all participants is locked. It will be used for a JNDA submission.

Data up to week 24 (specifically, data up to the date of visit 5 (week 24) or the date of withdrawal before week 24 visit for a given subject) will be used for outputs (i.e., tables/figures). The definition of the cut-off date for the interim analysis will be the date of Visit 5 (Week 24) for the last enrolled participant in this study. As for the AE data to be included in interim analyses, please also refer to the definition of AE assessment window ([11.3.2.1](#)).

The interim planned primary analyses will be performed after the completion of the following sequential steps for this Clinical Data Interchange Standards Consortium [CDISC] study:

1. All participants have completed the 24-week administration during treatment period (except for the premature withdrawals) as defined in the protocol.
2. All required database cleaning activities have been completed and interim DBR for the 24-week during treatment period has been declared by Data Management (DM).

3. System Independent (SI) data to Study Data Tabulation Model (SDTM) data conversion has been completed by Conversion Service Provider at interim Source Data Lock (SDL).
4. Randomisation codes have been distributed according to RandAll NG procedures
5. Interim Database freeze (DBF) on interim SDTM datasets has been declared by DM.

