6.1.5. Treatment Compliance

Treatment compliance will be assessed during the treatment period by dose group and total.

For the treatment period, the actual total number of doses received by each subject will be calculated as the sum of (dose counter start value – dose counter stop value) over all inhalers dispensed to the subject during the treatment period and returned prior to or at the EOT/EW visit, and percentage compliance will be calculated as follows:

$$\text{Treatment Compliance} = \frac{\text{total number of doses received}}{\text{treatment stop date} - \text{treatment start date} + 1} \times 100.$$

In interim analysis, treatment compliance will be calculated based on data until the day before visit 5 (i.e., treatment stop date will be replaced with the day before visit 5). Details on the derivations are provided in Section 11.6.2.

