8.1. Extent of Exposure

Overall extent of exposure to study treatment will be summarized in increments of 4 weeks for ≥ 1 day, ≥ 4 weeks, ≥ 8 weeks, ≥ 12 weeks, ≥ 16 weeks, ≥ 20 weeks, ≥ 24 weeks, ≥ 28 weeks, ≥ 32 weeks, ≥ 36 weeks, ≥ 40 weeks, ≥ 44 weeks, ≥ 48 weeks, ≥ 52 weeks, in addition to providing summary statistics and total treatment exposure (person-year).

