11.6.3. Safety

Adverse Events
Adverse Event Rate
Event rate per thousand person-years will be displayed for AE data in separate tables as listed in Section 11.11.5 and Section 11.11.6. Event rate per thousand person-years will be calculated as the number of events x 1000 divided by the total participant exposure during the time-period of interest (i.e., during treatment period).
AE'S OF Special Interest
Adverse events of special interest have been defined as AEs which have specified areas of interest. These consist in groupings of preferred terms based on the MedDRA dictionary version used in each reporting effort. Subgroups may be defined, based on relevant combination of preferred terms, or on Standardized MedDRA queries (SMQ).

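### Do the one-day inconsistencies around Visit 5 in the SAP (interim AE cut, interim person-time, dose at AE) call for a change?

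*SAP*

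**What the plan says.** Three places in the SAP deal with the Visit 5 day.

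- **Interim AE cut.** Section 3.1 sets interim outputs at "data up to the date of visit 5 (week 24) or the date of withdrawal before week 24 visit for a given subject", then adds: "As for the AE data to be included in interim analyses, please also refer to the definition of AE assessment window", pointing to 11.3.2.1. There the rule is that "data up to the day before visit 5 (week 24 visit) will be used for AE/SAE related analyses". The parent section 11.3.2 says, however, that "Section 11.3.2.1 and Section 11.3.2.2 are applicable only AE summaries by period", which at the interim means Table 2.9.
- **Interim person-time.** A note in 11.3.2.1 says that "data except for AE/SAEs up to the day OF visit 5 (week 24 visit) will be used in interim analyses". Section 8.1 asks for total person-years without an interim end date. Section 11.6.3 defines the AE rate as "the number of events x 1000 divided by the total participant exposure during the time-period of interest", explained as the treatment period. Section 6.1.5 does give an interim stop, but only for compliance: "treatment compliance will be calculated based on data until the day before visit 5".
- **Final dose-at-AE analysis, switchers only.** Section 5.1.2.2 ends the 100/62.5/25 period on the eve of Visit 5 and starts the 200/62.5/25 period once the Visit 5 day has passed. The table in 11.3.2.3 starts 200/62.5/25 on the Visit 5 day itself.

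**The concern.** AEs and SAEs are the primary endpoint, and the Week 24 summary supports a Japanese submission, so its tables ought to agree with one another. A programmer who takes 11.3.2 at its word would stop Table 2.9 on the eve of Visit 5 and let the other interim AE tables run through Visit 5. Table 2.3 could then hold events that Table 2.9 omits.

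In rate Tables 2.4, 2.7, 2.12 and 2.15, the events would stop one day before the exposure, which biases the rates downward.

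In the final analysis, an AE starting on a switcher's Visit 5 day would have no dose under the literal wording of 5.1.2.2. The dose-at-AE tables exist because the Japanese authority asked for them.

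**Working it through.** The plan states no figure on this point, so there is none to reproduce. The inputs are the Visit 5 day (nominal Day 169, window -5/+2, hence Day 164 to 171, from the Schedule of Activities), the rate formula in SAP 11.6.3, and 110 participants (Protocol 10.1) for illustration only.

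**1. Scope of the interim AE cut.** By title, Tables 2.2 to 2.16 are 15 AE tables. Adding MACE (2.17, 2.18) makes 17, and on-treatment pneumonia (2.34) makes 18. If 11.3.2 alone governed, all but Table 2.9 would fall back on the general rule in 3.1. Two things point the other way:
- 3.1 refers interim AE data to 11.3.2.1 without limiting this to by-period tables.
- 11.3.2.1 states the eve-of-Visit-5 stop for AE/SAE data twice, and sets it expressly against the Visit 5 stop for all other data.

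Section 5.1.1 supplies the reason: the interim excludes data after a switch and reports by allocated dose. Switching happens at Visit 5. The restriction in 11.3.2 fits most naturally as a remark about the week bins.

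**2. Person-time.** Let d be the Visit 5 day. If events are counted over d - 1 days and exposure over d days, the rate is multiplied by (d - 1)/d, a shortfall of 1/d.

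| Visit 5 day | Shortfall 1/d |
|---|---|
| 164 | 0.61% |
| 169 | 0.59% |
| 171 | 0.58% |

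As an illustration, assume 110 participants, no withdrawals, Visit 5 on Day 169, 365.25 days per year and 50 events:
- Exposure to Day 168: 110 × 168 / 365.25 = 50.60 person-years; 50 × 1000 / 50.60 = 988.2 per 1000.
- Exposure to Day 169: 110 × 169 / 365.25 = 50.90 person-years; 50 × 1000 / 50.90 = 982.4 per 1000.

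The difference is 0.30 person-years. Participants who withdraw before Visit 5 do not contribute the extra day, so the true effect is smaller.

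**3. Exposure classes in Table 2.1.** Twenty-four weeks is 24 × 7 = 168 days. Counting exposure as stop - start + 1 (the form used for compliance; an assumption here), a Visit 5 on Day 168 gives 168 days if exposure ends that day and 167 if it ends the day before. Of the eight in-window days, only Day 168 changes class. The note on non-AE data in 11.3.2.1 implies the first count.

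**4. Dose at AE.** Section 11.3.2 names 11.3.2.3 as the section for this approach, and its table leaves no gap. The by-period table for switchers in 11.3.2.2 also starts its post-switch window on the Visit 5 day and gives the day of the switch as the reason. Section 5.1.2.2 is the outlier and reads as loose wording for a period that begins on that day. The affected data are one day per switcher, in 14 final tables by title (12.4, 12.5, 12.9, 12.10, 12.12, 12.13, 12.16, 12.17, 12.24, 12.25, 12.28, 12.29, 12.31, 12.32). The number of switchers cannot be known in advance.

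**The case for a change.** The best case for a change is that the conflicts are literal, sit in the primary endpoint of a submission, and would cost a few sentences to remove. It has further support in Protocol 7.2: the Visit 5 dose is held until clinic staff give the instruction, so a switcher may first inhale the new strength that day. Exposure running through Visit 5 could then put one day on 200/62.5/25 into the interim 100/62.5/25 column. Read without 3.1, the treatment period in 11.4.1 even runs to Visit 7, and the interim denominator could be 365/168 = 2.17 times too large.

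The last point fails, because 3.1 cuts each participant's interim data at Visit 5. The stray day on the new strength is the same single day already sized above.

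What stands is that 11.3.2 and 11.3.2.1 differ in words, that the SAP does not explicitly match interim person-time to the AE cut, and that 5.1.2.2 disagrees with 11.3.2.3. For the first and third, the SAP itself shows which reading operates. For the second, either end date gives practically the same rate.

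**Conclusion.** No change is called for. Two of the three discrepancies are drafting slips that the SAP's own cross-references resolve: the interim AE cut falls on the eve of Visit 5 for all AE/SAE data, and the switchers' Visit 5 day counts as 200/62.5/25. The third is a gap of at most one day in interim person-time, worth about 0.6% of a descriptive rate; a programmer can take either day without harm.

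The study has no hypothesis and displays no treatment comparison, and AEs left out of the interim are reported in the final analysis. No conclusion depends on the choice.

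This rests on 3.1 limiting interim data to Visit 5 and on visits falling near their scheduled day. SAP 11.3.1 keeps out-of-window measurements, so 0.58% to 0.61% is not a strict range, but 1/d moves slowly with d. It also assumes the analysts follow the specific rules in 11.3.2.1 and 11.3.2.3 over the looser sentences in 11.3.2 and 5.1.2.2.

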11.3.2.2. In Final Analyses

For treatment group of “only FF/UMEC/VI 100/62.5/25” and “only FF/UMEC/VI 200/62.5/25”, the table below will be applied (see Section 11.5.1 for treatment group description).

Analysis Window		Analysis Timepoint
Beginning Timepoint	Ending Timepoint	
Day 1	Day 84	Week 0-12
Day 85	Day 168	Week 13-24
Day 169	Day 252	Week 25-36
Day 253	Day 365 Or The day of visit 7 (week 52 visit) if this is later than Day 365	Week 37-52
Day 1	Day 168	Week 0-24
Day 169	Day 365 Or The day of visit 7 (week 52 visit) if this is later than Day 365	Week 25-52

For treatment group of “FF/UMEC/VI 100/62.5/25 to FF/UMEC/VI 200/62.5/25”, the table below will be applied (see Section 5.1 for treatment group description). The reason to use separate analysis window for “FF/UMEC/VI 100/62.5/25 to FF/UMEC/VI 200/62.5/25” is to consider the day of switched treatment (i.e. the day of week 24).

Analysis Window		Analysis Timepoint
Beginning Timepoint	Ending Timepoint	
Day 1	Day 84	Week 0-12
Day 85	The day before visit 5 (week 24 visit)	Week 13-24
The day of visit 5 (week 24 visit)	Day 252	Week 25-36
Day 253	Day 365 Or The day of visit 7 (week 52 visit) if this is later than Day 365	Week 37-52
Day 1	The day before visit 5 (week 24 visit)	Week 0-24
The day of visit 5 (week 24 visit)	Day 365 Or The day of visit 7 (week 52 visit) if this is later than Day 365	Week 25-52

11.3.2.3. By dose at the time of onset of the AEs (by dose at AE)

For treatment group of “only FF/UMEC/VI 100/62.5/25” and “only FF/UMEC/VI 200/62.5/25”, the approach “by dose at AE” will summarize AEs during treatment period as each dose.

For treatment group of “FF/UMEC/VI 100/62.5/25 to FF/UMEC/VI 200/62.5/25”, the table below will be applied for an approach “by dose at AE” analyses.

Analysis Window		By dose at AE
Beginning Timepoint	Ending Timepoint	
Day 1	The day before visit 5 (week 24 visit)	As FF/UMEC/VI 100/62.5/25
The day of visit 5 (week 24 visit)	Day 365 Or The day of visit 7 (week 52 visit) if this is later than Day 365	As FF/UMEC/VI 200/62.5/25

11.4. Appendix 4: Study Phases and Treatment Emergent Adverse Events

11.4.1. Study Phases

Assessments and events will be classified according to the time of occurrence relative time of assessment.

Study Phase	Definition
Screening/Run-In period	Visit 1 date \leq Assessment Date/Time $<$ Date of study treatment start date
Treatment period	Study Treatment Start Date \leq Date \leq Date of Visit7/EOT or EW
Follow-up period	Date $>$ Date of Visit7/EOT or EW

11.4.1.1. Study Phases for Concomitant Medication

Study Phase	Definition
Prior	If medication end date is not missing and is before study treatment start date
Concomitant	Any medication that is not a prior

NOTES:

- Please refer to [Appendix 7](#): Reporting Standards for Missing Data for handling of missing and partial dates for concomitant medication. Use the rules in this table if concomitant medication date is completely missing.

11.4.2. Treatment Emergent Flag for Adverse Events

Flag	Definition
Treatment Emergent	
 • If AE onset date is on or after treatment start date & on or before treatment stop date. • Study Treatment Start Date \leq AE Start Date \leq Study Treatment Stop.

NOTES:

- If the study treatment stop date is missing, then the AE will be considered to be On-Treatment.

11.5. Appendix 5: Data Display Standards & Handling Conventions

11.5.1. Reporting Process

Software	

 The currently supported versions of SAS software will be used. 	
Reporting Area	
HARP Server	¥¥uk1salx00175.corpnet2.com¥
HARP Compound	Primary (interim) analysis: ¥arenv¥arprod¥gsk2834425¥mid207236¥primary_01 Final analysis: ¥arenv¥arprod¥gsk2834425¥mid207236¥final_01
Analysis Datasets	

 Analysis datasets will be created according to CDISC standards (SDTM IG Version 3.2& ADaM IG Version 1.0). 	
Generation of RTF Files	

 RTF files will not be generated 	

11.5.2. Reporting Standards

General

 The current GSK Integrated Data Standards Library (IDSL) will be applied for reporting, unless otherwise stated (IDSL Standards Location: https://spope.gsk.com/sites/IDSLLibrary/SitePages/Home.aspx): 
 4.03 to 4.23: General Principles 5.01 to 5.08: Principles Related to Data Listings 6.01 to 6.11: Principles Related to Summary Tables 7.01 to 7.13: Principles Related to Graphics
Formats

 GSK IDSL Statistical Principles (5.03 & 6.06.3) for decimal places (DP's) will be adopted for reporting of data based on the raw data collected, unless otherwise stated. Numeric data will be reported at the precision collected on the eCRF. The reported precision from non eCRF sources will follow the IDSL statistical principles but may be adjusted to a clinically interpretable number of DP's.
Planned and Actual Time

 Reporting for tables, figures and formal statistical analyses: 
 Planned time relative to dosing will be used in figures, summaries, statistical analyses and calculation of any derived parameters, unless otherwise stated. The impact of any major deviation from the planned assessment times and/or scheduled visit days on the analyses and interpretation of the results will be assessed as appropriate. Reporting for Data Listings: 
 Planned and actual time relative to study drug dosing will be shown in listings (Refer to IDSL Statistical Principle 5.05.1). Unscheduled or unplanned readings will be presented within the subject's listings.
Unscheduled Visits

 Unscheduled visits will not be included in summary tables and/or figures except as part of a 'worst case post-baseline' assessment.

• All unscheduled visits will be included in listings.	
Descriptive Summary Statistics	
Continuous Data	Refer to IDSL Statistical Principle 6.06.1
Categorical Data	N, n, frequency, %
Graphical Displays	
• Refer to IDSL Statistical Principals 7.01 to 7.13.	

